5.10. Abdominal Magnetic Resonance Imaging

Abdominal MRI will be performed at the time points specified in [Appendix B](#) to quantify organ volume, and to evaluate the aorta and other intra-abdominal vessels for atherosclerosis. All imaging scans will be acquired by an MRI technician or other qualified individual using standardized imaging protocols and will be read by a central reader, who will be blinded to time point of image acquisition.

Imaging scans are required for all subjects, except those who have internal metal medical devices or other non-removable metal items that may pose a risk to subject safety (e.g., cardiac pacemakers, aortic or cerebral aneurysm clips, artificial heart valves, ferromagnetic implants, shrapnel, wire sutures, joint replacements, bone or joint pins/rods/screws/clips), and children in whom sedation would be required but is medically contraindicated. In such populations, abdominal ultrasound will be substituted for an MRI.

Detailed instructions on image acquisition and analysis will be provided in the Imaging Manual.

5.11. Carotid MRI

Carotid MRI will be performed at the time points specified in [Appendix B](#) to quantify degree of stenosis in the carotid arteries. All imaging scans will be acquired by an MRI technician or other qualified individual using standardized imaging protocols and will be read by a central reader, who will be blinded to time point of image acquisition.

Imaging scans are required for all subjects, except those who have internal metal medical devices or other non-removable metal items that may pose a risk to subject safety (e.g., cardiac pacemakers, aortic or cerebral aneurysm clips, artificial heart valves, ferromagnetic implants, shrapnel, wire sutures, joint replacements, bone or joint pins/rods/screws/clips), and children in whom sedation would be required but is medically contraindicated.

Detailed instructions on image acquisition and analysis will be provided in the Imaging Manual.

5.12. Liver Biopsy

Liver biopsies will be obtained for subjects who are ≥ 18 years of age at Screening and at Week 48, or at the end of study treatment in the case of early withdrawal after at least 20 weeks of treatment. A liver biopsy will also be obtained on an optional basis at Week 96 after subject and/or legal guardian consent (as appropriate).

Biopsies for subjects < 18 years of age will be performed where local regulations permit. Liver biopsies will be obtained at Screening and at Week 48, or at the end of study treatment in the case of early withdrawal after at least 20 weeks of treatment. A liver biopsy will also be obtained on an optional basis at Week 96 after subject assent (as appropriate) and legal guardian consent.

If a subject had a liver biopsy within 26 weeks prior to Screening as part of clinical standard of care, and this historical biopsy is deemed adequate for histological assessment of liver pathology in this study (see SOM for minimum criteria), then a biopsy procedure will not be required at Screening.

Liver biopsy procedures will be performed according to the local institutional practices by a qualified professional. In those subjects with advanced liver disease, the biopsy must be obtained using the transjugular method, where local regulations and facilities permit, so the hepatic venous pressure gradient (HVPG) can be measured and collected during the procedure.

All biopsies collected during this study will be evaluated centrally by pathologists who will be blinded to assessment time point. Any biopsy done for other medical reasons during the course of the study will also be evaluated by central pathologists (stained and unstained samples). Blinded histological evaluation will include a comparison of overall disease activity at Baseline and Week 48. If applicable, comparisons will also be made with biopsies obtained at additional time points. Additional histological analysis of exploratory measures of disease activity may be performed, if tissue volume permits.

Refer to the Histopathology Manual for further details on the collection, processing, and evaluation of liver biopsies.

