3.2. Rationale for Study Design

Clinical studies are ongoing to evaluate the safety and efficacy of sebelipase alfa in subjects with LAL Deficiency. As noted in [Section 1.1.2](#), LAL Deficiency presents as a clinical continuum and the current clinical studies are designed to accommodate differences in the presentation and rapidity of progression.

Given the potential for variable presentation and progression of LAL Deficiency, it is important to expand the clinical experience by evaluating additional subjects not previously studied who are not eligible for ongoing clinical studies, such as subjects between 8 months and 4 years of age, subjects presenting with growth failure or other evidence of rapidly progressive disease that develops later than 6 months of age, previously transplanted subjects, subjects presenting with complications other than hepatic dysfunction, subjects with advanced liver disease or other complications that may put them at undue risk during the placebo controlled phase of a trial. The data from this study may provide supportive information on the activity of sebelipase alfa on additional less common clinical manifestations of LAL Deficiency.

Studies in a highly relevant animal disease model of LAL Deficiency have demonstrated favorable effects on growth and survival. A strong concordance was demonstrated between liver fat content (cholesterol esters and triglyceride), liver weight, and serum transaminases during both disease progression and in response to different doses of sebelipase alfa. In this model, treatment with sebelipase alfa was associated with substantial improvements in liver pathology, with complete resolution of abnormalities and restoration of normal liver architecture at maximally effective doses ([Leavitt et al., 2011](#)). To provide supportive data of this concordance in humans, the current study will evaluate liver histopathology at Baseline and at Week 48 (or at the end of treatment, if earlier than Week 48) in all adult subjects, and in pediatric subjects where local regulations allow. In order to minimize the need for this invasive procedure, a baseline biopsy will be performed only if acceptable historical liver histopathology data are not available (see [Section 5.12](#)).

An expanded treatment period was included in this study to ensure continued access to treatment for each subject until sebelipase alfa is registered and available in the region where the subject resides or is receiving treatment.

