4.6.2. Procedures for Discontinuation

If a subject is discontinued from the study, the subject or their parent or legal guardian will be asked about the presence of AEs. The date and reason(s) for discontinuation will be recorded in the eCRF. The date of discontinuation will be the date that the Investigator discontinues the subject from the study or that the subject notifies the Investigator of the decision to discontinue. The reason for discontinuation will be that identified by the Investigator or voluntarily reported by the subject. If a subject withdraws consent and does not voluntarily provide a reason for discontinuation, "withdrawal of consent" will be recorded in the eCRF.

A subject will be considered discontinued due to an AE if the subject received any infusion or partial infusion of study drug, but did not complete the study because of an AE, whether or not the AE is considered drug related.

Subjects who prematurely discontinue treatment in the study will have an end-of-study visit prior to withdrawal, and a follow-up call at least 4 weeks after the last infusion, whenever feasible (see [Appendix B](#) for a list of the assessments to be performed at this visit). Post-study SAEs

and IARs will be reported according to [Section 7.4](#) for all subjects prematurely discontinuing treatment in the study.

When a subject fails to return for scheduled assessments, efforts must be made to contact the subject (or the subject's parent or legal guardian) to determine a reason for the failure to return. If 2 or more consecutive visits are missed, the Investigator should contact the Sponsor to determine whether the subject will be allowed to continue on study. After all reasonable efforts to reach a subject (or the subject's parent or legal guardian) have been exhausted, the subject will be identified as lost to follow up in the eCRF.

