4.8. Subject Re-Screening

Subjects will be allowed to return for re-screening.

A subject will be re-consented if re-screening occurs outside of the 45-day screening window. In this case, all screening procedures must be repeated with the exception of LAL enzyme activity and DNA blood sampling, MRIs, biopsies, hepatic venous pressure gradient, transient elastography, and esophagogastroduodenoscopy (EGD). MRIs and biopsies must only be repeated if the previously obtained MRI or biopsy (either from an earlier screening visit or an acceptable historical biopsy procedure as per [Section 5.12](#)) was obtained more than 26 weeks prior to Screening.

5. Schedule of Assessments and Study Procedures

The type and frequency of study assessments is outlined in the schedule of assessments in [Appendix B](#). All study visits will be scheduled relative to Week 0. The Investigator may also conduct an unscheduled visit at any time during the study at his/her discretion. Assessments performed at an unscheduled visit will be symptom directed and will be recorded in the eCRF. Assessments performed only for subjects of a certain age are based on the subject's age on the date that informed consent is obtained, unless otherwise indicated below.

5.1. *Informed Consent/Assent*

The subject (or the subject's parent or legal guardian, if applicable) will be given a verbal explanation of the study, including information about the study drug and the study procedures, and will have all questions adequately addressed. The subject (or the subject's parent or legal guardian, if applicable) must sign and date a consent form that has been approved by the appropriate Institutional Review Board (IRB)/Independent Ethics Committee (IEC) before the screening procedures are initiated. All subjects (or their parents or legal guardians) will be given a copy of the signed and dated informed consent form. In addition, age-appropriate assent will be obtained as required from subjects who are of minor age according to local regulations.

5.2. *Subject Eligibility*

All subjects will be assessed for eligibility against the inclusion and exclusion criteria described in [Section 4.3](#) and [Section 4.4](#), and supportive clinical information collected.

5.3. *Medical History*

5.3.1. *Subject Medical History*

A complete medical history will be obtained for each subject at Screening, including the following:

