| | Week 100 ±7 days | Week 104 ±7 days | Week 108 ±7 days | Week 112 ±7 days | Week 116 ±7 days | Week 120 ±7 days | Week 124 ±7 days | Week 128 ±7 days | Week 132 ±7 days | Week 136 ±7 days | Week 140 ±7 days | Week 144 ±7 days | | |
| 12-lead ECG | | | | | | | | | | | | X ^P | X | |
| Physical Examination ¹ | | | X ^P | | | X ^P | | | X ^P | | | X ^P | X | |
| Weight | Every two weeks ^P | | | | | | | | | | | | X | |
| Abdominal MRI ² | | | | | | | | | | | | X ^P | X | |
| Carotid MRI | | | | | | | | | | | | X ^P | X | |
| Esophagogastroduodenoscopy ³ | | | | | | | | | | | | X ^P | | |
| Endoscopic biopsy ⁴ | | | | | | | | | | | | | | |
| Liver Biopsy ⁵ | | | | | | | | | | | | | X | |
| Hepatic Venous Pressure Gradient | | | | | | | | | | | | X ^P | X | |
| Transient elastography ⁶ | | | | | | | | | | | | X ^P | X | |
| HRQOL | | | | | | X ^P | | | | | | X ^P | X | |
| Clinical Laboratory⁷ | | | | | | | | | | | | | | |
| LAL Enzyme Activity (DBS) | | | | | | | | | | | | | X | |
| Liver Panel | | | X ^P | | | X ^P | | | X ^P | | | X ^P | X | |
| Lipid Panel | | | X ^P | | | X ^P | | | X ^P | | | X ^P | X | |
| Hematology, Electrolytes, Glucose, Creatinine | | | X ^P | | | X ^P | | | X ^P | | | X ^P | X | |
| Coagulation Panel | | | X ^P | | | X ^P | | | X ^P | | | X ^P | X | |
| Pregnancy Test ⁸ | X ^P | X ^P | X ^P | X ^P | X ^P | X ^P | X ^P | X ^P | X ^P | X ^P | X ^P | X ^P | X | |
| Anti-drug Antibody | | | X ^P | | | X ^P | | | X ^P | | | X ^P | X | |
| Urinalysis | | | X ^P | | | X ^P | | | X ^P | | | X ^P | X | |
| Macrophage Activation Markers | | | X ^P | | | X ^P | | | X ^P | | | X ^P | X | |
| HbA1c | | | X ^P | | | X ^P | | | X ^P | | | X ^P | | |
| CDT | | | | | | X ^P | | | | | | X ^P | | |
| Blood Exploratory Biomarkers | | | X ^P | | | X ^P | | | X ^P | | | X ^P | | |
| Vital Signs ⁹ | Every two weeks ^P | | | | | | | | | | | | X | |
| Sebelipase alfa Infusion ¹⁰ | Every two weeks | | | | | | | | | | | | | |
| Adverse Event Assessment | Continuous | | | | | | | | | | | | | |
| Concomitant | Continuous | | | | | | | | | | | | | |

| Assessments* | Expanded Treatment | | | | | | | | | | | | End of Study Visit (Early Withdrawal) | Follow-up Phone Call 4 Weeks (+7) days after last infusion |

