|------------------------------|--------------------|------------------|------------------|------------------|------------------|------------------|------------------|------------------|------------------|------------------|------------------|------------------|---------------------------------------|--|
| | Week 100 ±7 days | Week 104 ±7 days | Week 108 ±7 days | Week 112 ±7 days | Week 116 ±7 days | Week 120 ±7 days | Week 124 ±7 days | Week 128 ±7 days | Week 132 ±7 days | Week 136 ±7 days | Week 140 ±7 days | Week 144 ±7 days | | |
| Meds/Treatment ¹¹ | | | | | | | | | | | | | | |

*Note: All study visits will be scheduled relative to Day 0 (Baseline); consecutive infusions must be administered at least 7 days apart. Assessments performed for subjects of a certain age are based on the subject's age on the date that informed consent is obtained.

^P Pre-infusion

¹ All physical examinations will include assessment of liver and spleen size, lymphadenopathy, arterial disease, and skin manifestations of liver disease or dyslipidemia. Physical examination findings should drive additional functional assessments.

² Abdominal ultra-sound can be substituted if an abdominal MRI is medically contraindicated.

³ Esophagogastroduodenoscopy at Week 144 is optional.

⁴ Repeat endoscopic biopsy during the study is not required, however any biopsy performed will be recorded in the CRF.

⁵ The liver biopsy should be obtained via the transjugular method in those subjects with advanced liver disease, where local regulations and facilities permit, so the hepatic venous pressure gradient can be measured and collected during the procedure. Any biopsy done for other medical reasons during the course of the study will also be evaluated by central pathologists (stained and unstained samples). Subjects who have any prior liver biopsy unstained sections will be analyzed in the same method, if available.

⁶ Transient elastography will be performed in locales where technology is available.

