- ⁴ Liver biopsies will be obtained in subjects <18 years of age. The liver biopsy should be obtained via the transjugular method in those subjects with advanced liver disease, where local regulations and facilities permit, so the hepatic venous pressure gradient can be measured and collected during the procedure. Any biopsy done for other medical reasons during the course of the study will also be evaluated by central pathologists (stained and unstained samples). Subjects who have any prior liver biopsy unstained sections will be analyzed in the same method, if available.
- ⁵ Any endoscopic biopsy performed during the study will be recorded in the CRF.
- ⁶ Transient elastography will be performed in locales where technology is available.
- ⁷ Denver II assessments will be completed for subjects who are ≤6 years old during the screening period at the time of Informed Consent.
- ⁸ Age-appropriate health-related quality of life questionnaires will be completed prior to any other study procedures.
- ⁹ Refer to [Table 1](#) for a list of analytes in each laboratory panel. Subjects will refrain from ingestion of alcohol for 24 hours prior to collection of blood samples for lipid and liver panels. Labs will be drawn as blood volume and clinical status allow. See laboratory manual or SOM for details. Prior to any dose change, serum lipid, serum liver, hematology, chemistry, ferritin and hs-CRP shall be obtained; *ADA and PK assessments will be obtained on the day of any study drug dose change, as described in Section 5.9.4.* Serum lipid and serum liver assessments should be taken 4, 8, and 12 Weeks following any study-drug or lipid drug dose change.
- ¹⁰ For female subjects of childbearing potential only. Serum pregnancy test is required at Screening. Urine pregnancy tests at all designated visits thereafter.
- ¹¹ On the day of study drug dosing, vitals will be collected pre-dose, every 30 minutes (±10 min) during the infusion, and every 30 minutes (±10 min) from 0 to 2 hours after infusion. Beginning at Week 24, the post infusion period for vital sign monitoring may be shortened from 2 hours to 1 hour for subjects who have completed at least 22 weeks of treatment with no occurrence of moderate or severe IARs, contingent upon approval from the Sponsor.

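### Appendix B marks a liver biopsy at the early-withdrawal visit without the 20-week treatment minimum that Section 5.12 sets

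*Protocol*

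**What the plan says.** Protocol Section 5.12 sets the liver biopsy time points itself: Screening and Week 48, "or at the end of study treatment in the case of early withdrawal after at least 20 weeks of treatment". The same condition appears in the adult paragraph and in the pediatric one. For Week 96 the section says "A liver biopsy will also be obtained on an optional basis at Week 96", subject to consent.

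Appendix B, in the Expanded Treatment Period through Follow-up table of each schedule, marks a liver biopsy in the End of Study Visit (Early Withdrawal) column.

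- **Schedule I (adults), footnote 5** begins: "The liver biopsy should be obtained via the transjugular method in those subjects with advanced liver disease". It goes on to central reading and to earlier tissue sections.
- **Schedule II (children), footnote 4** begins: "Liver biopsies will be obtained in subjects <18 years of age". It then covers the same matters.

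Neither footnote states a minimum time on treatment.

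Section 4.6.2 gives subjects who stop treatment early an end-of-study visit whenever feasible, and refers to Appendix B "for a list of the assessments to be performed at this visit". The opening of Section 5 says: "The type and frequency of study assessments is outlined in the schedule of assessments in" Appendix B.

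The design rationale in Section 3.2 describes histopathology at Baseline and "at Week 48 (or at the end of treatment, if earlier than Week 48) in all adult subjects", and in children where local regulations allow. It gives no 20-week minimum either.

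**The concern.** The section that describes the procedure limits the exit biopsy to subjects with at least 20 weeks of treatment. The table that sites are told to use for the exit visit has no such limit. For a subject who leaves before 20 weeks, the two texts give different answers, and the protocol does not say which one prevails.

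What is at stake is patient burden and safety. Liver biopsy is invasive. In advanced liver disease it is to be done by the transjugular route where local regulations and facilities permit, and adults and children are both affected. Monitors would also lack a clear basis for deciding whether an omitted exit biopsy is a deviation.

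**Working it through.** The plan states no figure to reproduce, so the check is a reading of the table cells followed by a count of biopsies under each text.

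**1. Where the mark falls.** The expanded-period tables have 14 cells after the row label: 12 visits (Weeks 100 to 144, every 4 weeks), then the early-withdrawal visit, then the follow-up call. In both schedules the only mark in the liver biopsy row is in cell 13. It belongs to early withdrawal and is not a displaced Week 144 mark.

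**2. Which exits the column covers.** It is the only early-withdrawal column in each schedule. Section 4.6.2 applies Appendix B to all subjects who stop treatment prematurely, so an exit in the first weeks is handled by this column even though it sits in the table for the expanded period.

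**3. Biopsies per subject, counting one at Screening.**

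| Time of exit | Section 5.12 | Appendix B read alone | Difference |
|---|---|---|---|
| Before 20 weeks | 1 (Screening) | 1 + 1 = 2 (Screening, exit) | 2 − 1 = 1 |
| From 20 weeks, before Week 48 | 1 + 1 = 2 | 1 + 1 = 2 | 0 |

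If an acceptable historical biopsy replaces the Screening procedure, the first row becomes 0 against 1, and the difference is still 1. The disagreement identified here concerns exits before 20 weeks.

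**4. Effect on the analyses.** The primary objective is safety, and no primary analysis uses biopsy results. Section 5.12 compares histology at Baseline and Week 48. SAP Section 7 summarizes visits as collected, and SAP Section 7.5.1 tabulates biopsy scores by time point, descriptively. A biopsy at an exit before 20 weeks would not enter the Week 48 comparison.

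**5. Adult Week 96 label.** In Schedule I, Week 52 to Week 96, the liver biopsy is marked at Week 96 and footnote 5 does not say it is optional. Footnote 4 of the matching pediatric table does, and adult footnote 3 says so for esophagogastroduodenoscopy. Section 5.12 makes the Week 96 biopsy optional for both age groups, so this is a missing label.

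**The case against.** The best reply is that Section 5.12 is complete and specific, and simply qualifies the mark in the table. Sections 5.10, 5.11, 5.13 and 5.14 take their time points from Appendix B. Section 5.12 does not; it lists its own and states the 20-week condition twice. A careful reader would probably reconcile the texts that way. That carries weight as to what the sponsor intended. It does not remove the gap, because Section 4.6.2 sends sites to the table for exactly this visit and the table's footnotes are silent.

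A reader might go further than the documents allow in three ways.

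- **That every early leaver must be biopsied.** The end-of-study visit applies only whenever feasible, and biopsies in children only where local regulations permit. The schedule could lead to an uncalled-for biopsy; it does not compel one. Feasibility is still a different test from 20 weeks of treatment.
- **That Section 3.2 is a second, independent instruction for an early biopsy.** It is design rationale. Its next sentence speaks of minimizing this procedure and cites Section 5.12, though only about the baseline biopsy, so the citation does not bring in the 20-week rule. The wording is loose but is not an operative order.
- **That the adult Week 96 biopsy is mandatory.** A mark in this table does not by itself mean required: the endoscopic biopsy row is also marked at Week 96, while its footnote says repeat biopsy is not required. Section 5.12 supplies both the optional status and the consent condition.

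**Conclusion.** The inconsistency is real and minor. For exits before 20 weeks, the schedule marks a liver biopsy that Section 5.12 does not call for, in adults and in children. The size is one invasive biopsy per affected subject. The documents give no expected number of such exits, so no total can be stated.

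This rests on two readings: that the early-withdrawal column serves all premature exits, which Section 4.6.2 supports, and that Section 5.12 states the sponsor's intended rule, which its repetition for both age groups supports. The primary safety analysis and the Baseline to Week 48 histology comparison are unaffected. The wording of Section 3.2 and the missing adult Week 96 label are side notes to the same correction.

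**What to change.** Add one sentence to the liver-biopsy footnotes of the two expanded-period tables in Appendix B (Schedule I, footnote 5; Schedule II, footnote 4): *At early withdrawal, only after at least 20 weeks of treatment.*

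In the same amendment, as tidying:

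- put the same minimum into the Section 3.2 rationale, for example *if earlier than Week 48 and after at least 20 weeks of treatment*;
- add *A liver biopsy at Week 96 is optional* to footnote 5 of Schedule I, Week 52 to Week 96, matching the pediatric footnote and Section 5.12.

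The cost is a protocol amendment of wording only: three footnotes and one clause. Section 5.12 stays as it is and no procedure is added. The downside is no histology from exits before 20 weeks, which Section 5.12 does not ask for.
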